5.6 Definition of special population

Definition of special population is defined as below.

- **Children and adolescent and geriatrics**

Special population	Chinese character	Age
Children and adolescent	小兒	18 years or younger
Geriatrics	高齡者(老人)	65 years or older

- **Hepatic impairment**

Hepatic impairment in concurrent disease was recorded as 'Yes'.

- **Renal impairment**

Renal impairment in concurrent disease was recorded as 'Yes'.

5.7 Safety evaluation

- **Occurrence of adverse event**

- For adverse event (AE), adverse drug reaction (ADR), unexpected adverse event (UAE) and serious adverse event (SAE), the total number of subjects, the number of events, the occurrence rate and 95% confidence interval will be summarized.
- AE and ADR will be classified by the system-organ class (SOC) and preferred term (PT) using WHOART (WHO Adverse Reactions Terminology) for nth investigation report and MedDRA (Medical Dictionary for Regulatory Activities) for re-examination report, and summarized by the number of subjects, the occurrence rate and the number of events.
- The details of unexpected adverse event, serious adverse event and adverse event of subjects who are excluded from safety evaluation in accordance with paragraph 5.1.1 will be listed.
- Severity, causal relationship, actions taken regarding Pergoveris™ administration and progress of AE categorized by SOC and PT using WHOART for nth investigation report and MedDRA for re-examination report will be analyzed by presenting the number of events and

percentage. If there are several levels for severity, causal relationship, actions taken regarding Pergoveris™ administration and progress of the same AEs, the level that will be used for the analysis will be the worst one on subject level.

▪ **Factors that might affect the safety evaluation**

The occurrence of adverse event for each factor of demographics (age), baseline characteristics (concurrent disease, period for infertility, allergic history, previous assisted reproductive technology experience, luteinizing hormone, follicle stimulating hormone, previous treatments for infertility, concomitant medication), Pergoveris™ exposure (average daily dose, total duration, total dose) and special population (hepatic impairment, renal impairment) will be presented by the frequency and rate with 95% confidence interval. The AE rate for each factor will be analyzed using Pearson's chi-square test or Fisher's exact test.

Additionally, the occurrence of adverse event for all factors described above will be analyzed using multivariable logistic regression.

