8. Applied SOPs.....	14

1. Objective of PMS

To analyze safety and efficacy information on Pergoveris™ in post-marketing uses, as well as factors likely to influence safety and efficacy

Primary objective: To get safety information in subjects using Pergoveris™

- 1) Serious Adverse Event (SAE)
 - ① If causing death or threatening one's life
 - ② If hospitalization or prolonged duration of hospitalization is necessary
 - ③ If causing continuous or significant disability or dysfunction
 - ④ If causing congenital malformation or abnormality
 - ⑤ Other medically critical conditions
- 2) Adverse event/adverse drug reaction unexpected in precautions
- 3) Already known adverse drug reaction
- 4) Non-serious adverse drug reaction
- 5) Other safety/efficacy related information (influence upon clinical laboratory value, etc.)

2. Patient population

Women with serious deficiency of Luteinizing Hormone (LH) and Follicle-Stimulating Hormone (FSH) at less than 1.2 IU/L of endogenous serum LH

3. Sample size

A total of 600 cases or more shall be reported as per the number of report cases pursuant to the Paragraph 3 of Article 6 of the 'Re-examination Standards for New Drugs Etc.' (Ministry of Food and Drug Safety Notification No. 2014-61).

4. Study items

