5.2 General principle

Continuous variables will be presented as descriptive statistics (mean with standard deviation, median, minimum and maximum values). For categorical variables, the number and percentage of subjects for each category and overall will be reported. Percentages will be based on the number of subjects observed at each category. All p-values will be presented as four decimal places. Values other than p-value such as mean, standard deviation, percentage, etc. will be presented as two decimal places.

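### SAP 5.7 assigns a subject-level worst level to adverse event tables that count events, so recurrent events with differing levels may be dropped or relabelled

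*SAP*

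**What the plan says.** The point sits in SAP section 5.7, in the part on occurrence of adverse events.

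- **Unit of the tables.** Severity, causality, action taken and progress, by SOC and PT, "will be analyzed by presenting the number of events and" percentage (the sentence runs over a line break).
- **Trigger of the level rule.** "If there are several levels for severity, causal relationship, actions taken regarding Pergoveris™ administration and progress of the same AEs".
- **The rule itself.** In that case "the level that will be used for the analysis will be the worst one on subject level".
- **Neighbouring tables.** For AE, ADR, unexpected AE and SAE overall, "the total number of subjects, the number of events, the occurrence rate and 95% confidence interval will be summarized". The SOC/PT tables for AE and ADR are "summarized by the number of subjects, the occurrence rate and the number of events". Neither bullet carries a rule for combining repeated events.
- **Percentages.** The only general rule, in section 5.2, is based on subjects: "Percentages will be based on the number of subjects observed at each category". It says nothing about percentages of events.

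The dummy tables are placed in an annex (section 6) that is not part of the text at hand.

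**The concern.** A table of events needs one level for each event. A worst level per subject serves a table in which each subject appears once per term. Section 5.7 combines the two and does not say how, so two programmers could produce different tables from the same data, both in good faith.

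Two constructions are possible when a subject has the same term more than once at differing levels:

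- **Collapse.** The repeats become one record at the worst level. The table then counts subject-by-term records under an event label, and its total falls below the event counts given elsewhere in 5.7.
- **Relabel.** Every repeat stays in the table but takes the worst level. Totals agree, but mild events are shown as severe and unrelated events as related. If ADRs are AEs judged related, which is the usual meaning although this SAP does not define the term, the related events in the causality table can exceed the ADR event count in 5.7 and in Appendix 3-1 of section 5.9.

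At stake are the severity and causality profiles in a surveillance study whose primary objective is safety. The level rule does not touch the occurrence rates and their confidence intervals.

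**Working it through.** The SAP states no figure on this point, so there is none to reproduce. The check counts assumed data in three ways:

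- A: each event at its own level.
- B: all repeats of a term within a subject collapsed to one record at the worst level.
- C: all events kept, each given the subject's worst level for that term.

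**Step 1: small examples, one term (all data assumed). Entries are severe / total.**

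| Data | A | B | C |
|---|---|---|---|
| 8 subjects, 10 events: one subject mild, mild, severe; seven with one mild event | 1/10 = 10.00% | 1/8 = 12.50% | 3/10 = 30.00% |
| 8 subjects, 10 events: one subject with three severe; seven with one mild event | 3/10 = 30.00% | 1/8 = 12.50% | 3/10 = 30.00% |
| 10 subjects, 10 events: no recurrence, one severe | 1/10 = 10.00% | 1/10 = 10.00% | 1/10 = 10.00% |

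The first row shows both defects: two events lost under B, two mild events relabelled under C. Reading severe as related, C would report three related events against one ADR event. The second row shows that the share can also fall under a full collapse, but the rule as worded is not triggered there because the levels do not differ. The third row shows that nothing changes without recurrence.

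**Step 2: a range.** Assumed inputs: n = 60 affected subjects; probability p = 0.10 that an event is severe, independent between events; a share r of subjects with exactly one second event of the same term.

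- Events: n(1 + r). Records under B: n.
- Probability that at least one of two events is severe: 1 − (1 − p)² = 1 − 0.81 = 0.19.
- Severe share under B: [n(1 − r)p + nr × 0.19] / n.
- Severe share under C: [n(1 − r)p + 2nr × 0.19] / [n(1 + r)].

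For r = 0.40, B gives (3.60 + 4.56)/60 = 13.60% and C gives (3.60 + 9.12)/84 = 15.14%.

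| r | Events | Records under B | A | B | C |
|---|---|---|---|---|---|
| 0 | 60 | 60 | 10.00% | 10.00% | 10.00% |
| 0.05 | 63 | 60 | 10.00% | 10.45% | 10.86% |
| 0.10 | 66 | 60 | 10.00% | 10.90% | 11.64% |
| 0.20 | 72 | 60 | 10.00% | 11.80% | 13.00% |
| 0.40 | 84 | 60 | 10.00% | 13.60% | 15.14% |

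**Step 3: collapse only where the levels differ.** B merges every repeat, whereas the rule is triggered only by differing levels. With two levels (severe or not), two events differ with probability 2 × 0.10 × 0.90 = 0.18. At r = 0.40, 24 subjects have a second event, so 24 × 0.18 = 4.32 records are lost and 84 − 4.32 = 79.68 remain. Every lost record is a non-severe one, so the 84 × 0.10 = 8.40 severe events all stay: 8.40/79.68 = 10.54%. On this narrower collapse the distortion is small. C is the same either way, since relabelling alters nothing when the levels agree.

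**The case against.** The strongest defence is that the rule concerns one AE whose recorded level changed over time. Taking the worst level within that single event is ordinary practice and leaves event totals intact. This is possible, but it fits the wording poorly: the condition speaks of AEs in the plural and the worst level is taken on subject level, which points to several events of one term within a woman. Section 5.5 also sums exposure over several administration periods, so recurrence is at least plausible. If the harmless meaning was intended, a few words would say so.

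Other parts of the defence stand:

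- A reader might infer that these tables are bound to disagree with the event totals. The SAP does not support that. Totals differ only if a subject has the same AE again at a different level and the records are then collapsed. Under relabelling they agree.
- A reader might infer that the worst level per subject is applied across all AEs. The rule is limited to the same AE.
- Appendices 3-2 and 4 are not valid comparators: the first covers SAEs only, and the second pools spontaneous and literature reports. Only Appendix 3-1 can be compared, and only with the related rows of the causality table.
- Taking the worst level separately for severity, causality, action and progress is no error, since these are separate attributes.
- The unseen dummy tables may settle the unit and denominator. The sentence in 5.7 would still need to agree with them.

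**Conclusion.** The point holds in a limited form. Section 5.7 applies a subject-count rule to tables that count events and leaves open how to treat repeats. For recurrent events of one term at differing levels, the result is either missing events or overstated severe and related events.

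The size cannot be derived from the SAP, which gives neither a recurrence rate nor a severity distribution. On the assumptions above, with 5% to 40% of affected subjects having a second event, a true severe share of 10.00% becomes 10.45% to 13.60% under full collapse and 10.86% to 15.14% under relabelling. Collapse restricted to differing levels gives 10.54% at the 40% end. If levels within a subject tend to agree, the shifts are smaller. A single sparse term can move much more, as the step from 10.00% to 30.00% in the first example shows.

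It might be inferred that the primary safety results are compromised. They are not: the counts, rates and confidence intervals for AE, ADR, unexpected AE and SAE, and the SOC/PT occurrence tables, carry no such rule. Unexpected and serious AEs are also listed individually. Only descriptive cross-tabulations are affected, but they describe severity and causality in a safety study, and correcting them is cheap.

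**What to change.** Reword the last bullet on adverse event occurrence in section 5.7:

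1. In the event tables, count each event once, at its own severity, causality, action taken and progress, with the number of events as denominator. Totals then equal the 5.7 event counts.
2. Confine the worst-level rule to a single event whose level changed during its course, and define what counts as the same AE.
3. If a worst-case view is wanted, show it separately as the number of subjects by worst level per SOC and PT, with subjects as denominator. State the order from best to worst for causality, action and progress.
4. Add a denominator rule for event percentages to section 5.2, and check that the annexed dummy tables agree.

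The cost is SAP wording and, if the worst-case view is kept, one extra column block. No new data are needed.

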4.6 Concomitant medication

- 1) The name of concomitant medication (product)
- 2) Daily dose
- 3) Route of administration
 - ① PO (Per os)
 - ② IV (Intravenous)
 - ③ IM (Intramuscular)
 - ④ SC (Subcutaneous)
 - ⑤ SL (Sublingual)
 - ⑥ Ophthalmic
 - ⑦ TD (Transdermal)
 - ⑧ Others
- 4) Administration period: The administration start and end dates

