4.7 Safety items

Adverse event (including side effect) and serious adverse event, including onset date, disappearance date, severity, causal relationship with Pergoveris™, measures on administration of Pergoveris™, and progress

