5.3 Handling of missing data

No imputation of missing data will be performed for statistical analysis except for administration start date and end date.

If only partial information of administration start date or end date is available and is required for calculation of administration period, total dose as well as the average daily dose, the following methods will be used.

- If day is missing, the day will be imputed as day 1.
- If month is missing, the month will be imputed as January.
- If year is missing, the date will be considered as missing.

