5.4 Demographics and baseline characteristics

Demographics and baseline characteristics will be analyzed as below.

- **Variables that will be presented by frequency and percentage**

Age group, concurrent disease, allergic history, period for infertility, causes for infertility*, previous ART experience, ART procedure*, levels of serum Luteinizing Hormone (LH), levels of serum Follicle Stimulating Hormone (FSH), previous treatments for infertility

* Multiple responses

- **Variables that will be presented by descriptive statistics (mean with standard deviation, median, minimum and maximum values)**

Age, period for infertility, previous ART experiences, serum Luteinizing Hormone (LH), serum Follicle Stimulating Hormone (FSH)

- **Variables that will be classified by ATC code**

- Previous treatments for infertility: The frequencies and percentages of subjects having previous treatments for infertility as well as previous treatments for infertility classified by ATC (Anatomical Therapeutic Chemical) code will be presented.

- Concomitant medication: The frequencies and percentages of subjects having concomitant medications as well as concomitant medications classified by ATC code will be presented.

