5.5 Pergoveris™ exposure

Pergoveris™ exposure will be analyzed as below.

- **Administration period**

Administration period is defined as the sum of each administration period and will be summarized as descriptive statistics. Also, the administration period will be classified as two levels (\leq median, $>$ median) and presented by the frequency and percentage for each level.

- **Total dose**

Total dose is defined as the sum of total doses on each administration period and will be summarized as descriptive statistics. Also, the total dose will be classified as two levels (\leq median, $>$ median) and presented by the frequency and percentage for each level.

- **Average daily dose**

Average daily dose is defined as total dose divided by administration period and will be summarized as descriptive statistics. Also, the average daily dose will be classified as two levels (\leq median, $>$ median) and presented by the frequency and percentage for each level.

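### Section 5.7 uses concomitant medication as a baseline factor for adverse events but ties it to no date, so a drug given to treat an event could count as exposure

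*SAP*

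**What the plan says.** Section 5.7 lists the factors for the AE analysis and puts concomitant medication among the "baseline characteristics (concurrent disease, period for infertility, allergic history, previous assisted reproductive technology experience, luteinizing hormone, follicle stimulating hormone, previous treatments for infertility, concomitant medication". The AE rate is compared across each factor by Pearson's chi-square or Fisher's exact test. A model then takes in the whole list: "Additionally, the occurrence of adverse event for all factors described above will be analyzed using multivariable logistic regression".

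Section 5.4, also under a baseline heading, says how the variable is summarised: "The frequencies and percentages of subjects having concomitant medications as well as concomitant medications classified by ATC code will be presented". This counts any subject with a recorded drug, at any time.

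Section 4.6 lists the drug name, daily dose, route and "Administration period: The administration start and end dates". Section 4.5 lists the Pergoveris start and end dates, and section 4.7 lists the AE onset date. No rule uses these dates to decide which drugs count as the factor. The items in 4.6 include no reason for use.

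**The concern.** A factor that is supposed to influence AEs should be fixed before they can occur. The SAP labels this one as baseline but defines it as any recorded use. A subject who takes nothing at the start, has an AE and receives a drug for it would then fall in the medicated group because of the AE. Adjusting for age, hormone levels or other covariates does not help, since the outcome has created the exposure.

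The SAP's stated objective includes factors likely to influence safety. A low p-value or raised odds ratio for concomitant medication could be reported against that objective when it shows only that AEs were treated.

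**Working it through.** **Inputs.** N = 600 is the minimum in SAP section 3. The SAP gives no AE rate, no frequency of concomitant use and no share of AEs treated, so these are assumptions and are varied. It states no significance level; two-sided 5% is assumed, in line with its 95% confidence intervals. No figure in the plan bears on this point, so there is none to reproduce.

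**Model.** Let *u* be background use, unrelated to AEs, and *f* the share of subjects with an AE who receive a recorded drug for it. Then

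- P(medicated | no AE) = u
- P(medicated | AE) = u + (1 − u)f
- odds ratio = [u + (1 − u)f] / [u(1 − f)]

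The true odds ratio is 1.

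**Worked case: u = 0.30, f = 0.5, AE rate 5%.** Of 600 subjects, 30 have an AE and 570 do not.

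- P(medicated | AE) = 0.30 + 0.70 × 0.5 = 0.65, giving 19.5 medicated and 10.5 unmedicated.
- Without an AE: 171 medicated and 399 unmedicated.
- AE rate: 19.5/190.5 = 10.2% medicated, 10.5/409.5 = 2.6% unmedicated.
- Odds ratio: (19.5 × 399)/(171 × 10.5) = 4.33.
- Pearson chi-square on these expected counts: 600 × (7780.5 − 1795.5)² / (190.5 × 409.5 × 30 × 570) = 16.1, against a critical value of 3.84.

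**Simulated false significance** (10,000 replicates per cell; Pearson, or Fisher if any expected count is below 5; AE rate 5%):

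| Background use | 30% | 60% | 80% | 90% | 95% |
|---|---|---|---|---|---|
| Half of AEs treated | 97% | 62% | 22% | 3% | <1% |
| A quarter treated | 52% | 18% | 7% | 2% | 1% |
| A tenth treated | 15% | 6% | 4% | 2% | 2% |
| None treated | 5% | 5% | 5% | 3% | 2% |

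**Expected odds ratio from the formula:**

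| Background use | 30% | 60% | 80% | 90% | 95% |
|---|---|---|---|---|---|
| Half treated | 4.3 | 2.7 | 2.3 | 2.1 | 2.1 |
| A quarter treated | 2.1 | 1.6 | 1.4 | 1.4 | 1.4 |
| A tenth treated | 1.4 | 1.2 | 1.1 | 1.1 | 1.1 |

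**Other AE rates, half treated, same order of use.** At 2% the figures are 67/23/2/<1/<1%. At 10% they are 100/89/48/19/3%.

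**Why the test goes quiet at high use.** At u = 0.95 and f = 0.5 about 0.05 × 570 + 0.025 × 30 = 29 subjects are unmedicated. Even no AE among 29 has probability of about 0.95²⁹ = 0.23, so the test can hardly reject in that direction. The odds ratio remains biased.

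**Regression.** Five independent binary covariates were added, with 15% unrelated later drug starts among subjects not medicated at baseline (Wald test, 1,000 replicates, AE rate 5%). False significance at use of 30/60/80/90% was about 88/44/2/<1% with half treated and 34/14/2/1% with a quarter. Adjustment therefore does not remove the problem where it is large. With the factor limited to drugs started by the first dose, it was no more than about 5%.

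**Subjects whose dates cannot be ordered.** Subjects treated for an AE have an extra drug record, so they have more chance of an incomplete date. Suppose such subjects form a third tested category, with 5/10/20% of drug dates incomplete (assumed), 30% use, half of AEs treated and a 5% AE rate. False significance is then 13/16/26%. Left out of the test, it is about 5–7%.

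**The case against.** The strongest objection is that the premise lies outside the SAP. The bias needs AE treatments to be recorded as concomitant medication, and the protocol or case report form, neither shown, may settle that or set a recording period. The dummy tables, where factor categories might appear, are not shown either. The baseline label in 5.4 and 5.7 may also be meant as a restriction.

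This makes the problem conditional but does not remove it. What is recorded may be a matter for the form. How recorded drugs become an analysis factor is for the SAP, which fixes comparable rules elsewhere, such as median splits for exposure and date imputation. Here it gives a label, a definition that does not match the label, and no reference to a window.

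The second objection is that the size rests on assumptions. This population is having infertility procedures, so high background use is plausible, and the test would then seldom mislead. That stands; the biased odds ratio remains.

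A reader might go further in two directions that the document does not support:

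- **Total duration and total dose.** Section 5.5 builds these from realised administration ("Administration period is defined as the sum of each administration period"; "Total dose is defined as the sum of total doses on each administration period"), so an AE that stops treatment could shorten them. But the SAP openly labels them exposure, not baseline. Relating AEs to realised exposure is a legitimate aim, and part of any association may be real. This is a debatable trade-off, not a mismatch between label and definition.
- **Date imputation.** Section 5.3 says "If day is missing, the day will be imputed as day 1", which might seem to disturb the ordering of drug starts and first dose. That rule is confined to dates needed for administration period, total dose and average daily dose. It does not govern this factor.

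**Conclusion.** The point holds as a minor one. The SAP calls concomitant medication a baseline factor, defines it as any recorded use and ties it to no date. If AE treatments are recorded under 4.6, the AE can create the exposure, and neither the univariate tests nor the regression repairs that.

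The size depends on rates the SAP does not give. At an assumed 5% AE rate, false significance ranges from about 97% (30% use, half of AEs treated) to the nominal level or below (use near universal, or a tenth treated at 80% use or more). At near-universal use the odds ratio is still inflated, to about 2.1 if half are treated and 1.1 if a tenth are.

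A reader might infer that the safety results as a whole are biased, or that a false finding is certain. Neither follows. Overall AE, ADR and SAE incidence do not use this factor, and whether it misleads at all depends on recording practice.

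**What to change.** In section 5.7, define the factor as concomitant medication started on or before the first Pergoveris dose, using the dates listed in 4.5 and 4.6. Report subjects whose dates cannot be ordered descriptively, and leave them out of the test and the regression for this factor.

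The first dose is a better cut than AE onset. It applies alike to subjects with and without an AE, whereas onset exists only for those with one.

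The cost is a short definition in 5.7 and one derived variable from dates already collected. Drugs started after the first dose but before an AE are no longer tested, and a few subjects with incomplete dates drop out of this comparison.

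### Whole-course duration and total dose are tested as factors for adverse events and follicular growth, although an adverse event, and possibly response, can itself set them

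*SAP*

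**What the plan says.** Section 1 of the SAP sets the aim of analysing safety and efficacy "as well as factors likely to influence safety and efficacy". Section 3 sets the size by regulation: "A total of 600 cases or more shall be reported".

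Section 5.5 defines exposure over the complete course:
- Duration: "Administration period is defined as the sum of each administration period".
- Total dose: "Total dose is defined as the sum of total doses on each administration period".
- Average daily dose: "Average daily dose is defined as total dose divided by administration period".

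Each is split at the observed median; for duration, "the administration period will be classified as two levels". Sections 5.7 and 5.8 use the term total duration without defining it. The administration period of 5.5 is the only duration measure in the SAP, so I take the two to be the same.

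Section 5.7 (AE occurrence) and section 5.8 (follicular growth) then list "Pergoveris™ exposure (average daily dose, total duration, total dose) and special population" among the factors. Each factor is tested by Pearson's chi-square or Fisher's exact test, and all factors enter a multivariable logistic regression.

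For each AE, section 4.7 collects the onset date, the causal relationship and "measures on administration of Pergoveris™, and progress". Section 5.7 tabulates the action taken on administration. Section 4.8 lists hCG administration and follicular growth as efficacy items, but no section says what ends a course.

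**The concern.** A factor that is said to influence an outcome should be fixed before that outcome occurs. Whole-course duration and total dose are not.

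**Safety.** The SAP itself provides for an AE changing administration. A course stopped for an AE is short because of the AE. Doses given after onset also count as exposure, although they cannot have caused that AE. The first effect makes longer courses look safer.

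**Efficacy.** If follicular response, or the lack of it, influences how long treatment runs, response sets duration. The SAP is silent on this, so this half is conditional.

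Adjusting for the other listed factors does not remove the dependence. Nor would replacing the median split by a continuous term, or entering only one exposure variable. At stake is the Section 1 aim of identifying influencing factors: a table could report treatment length as protective, or as lowering effectiveness, when it does neither.

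**Working it through.** The SAP gives no alpha, power, AE rate or stopping rate, so there is no stated figure to reproduce. The numbers below are simulations that illustrate the mechanism.

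**Inputs from the SAP:** n = 600 (section 3), median split (5.5), Pearson chi-square (5.7, 5.8).

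**Assumed inputs:** two-sided 0.05, uncorrected test, AE risk 10% and independent of duration, a given share of on-treatment AEs stopping the course at onset. Two onset patterns were used: (A) every AE falls uniformly within the course, whole-day durations about normal(10, 3); (B) onset is uniform over 30 days, durations 6–14 days.

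| AEs that stop treatment | A: AE rate ≤ / > median | A: p<0.05 | B: AE rate ≤ / > median | B: p<0.05 |
|---|---|---|---|---|
| 0% | 10% / 10% | 5% | 10.0% / 10.0% | 5.2% |
| 5–10% | – | about 5–8% | – | between the rows above and below |
| 25% | 11.4% / 8.2% | about 25% | 10.5% / 9.2% | 8.3% |
| 50% | 12.7% / 6.3% | 75% | 11.2% / 8.5% | 17–19% across runs |
| 100% | – | – | 12.4% / 6.9% | 61.3% |

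**Check by hand.** With w the share at or below the median, the overall 10% fixes w. Then SE = √[0.1 × 0.9 × (1/n₁ + 1/n₂)], and the rejection rate is about Φ(z − 1.96).
- A, 50%: w = (10 − 6.3)/(12.7 − 6.3) = 0.578, so groups of 347 and 253. SE = 0.0248, z = 0.064/0.0248 = 2.58, and Φ(0.62) = 0.73. The simulation gave 75%.
- A, 25%: w = 1.8/3.2 = 0.5625, so about 338 and 262. SE = 0.0247, z = 0.032/0.0247 = 1.30, and Φ(−0.66) = 0.25.
- B, 50%: w = 1.5/2.7 = 0.556, so 333 and 267. SE = 0.0246, z = 0.027/0.0246 = 1.10, and Φ(−0.86) = 0.19.

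The results depend on small choices. With days treated as continuous, pattern A gives 33% and 89% instead of 25% and 75%. Administration dates give whole days, so I use the whole-day figures.

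**Time at risk adds a second distortion.** Suppose AEs are counted on treatment only, with a constant daily hazard (10% over 10 days). With no stopping, the rates are 12.3% above the median and 8.2% at or below it (39.0% rejection), simply because longer courses allow more time for an AE. With 25% stopping the two effects cancel (10.1% vs 9.9%, 5.3%). With 50% stopping the sign reverses (7.7% vs 11.7%, 36.3%).

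**Follicular growth.** Assumed: 80% response, no effect of duration, responders stop when they respond.

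| Non-responders | Effective rate > median | ≤ median | p<0.05 |
|---|---|---|---|
| all continue longer | 49.9% | 100% | 100% |
| half and half | 76.3% | 82.8% | 51% |
| all stopped early | 100% | 63.0% | 100% |

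The direction depends only on the stopping pattern. The simulations cover duration; total dose accumulates with it, so the same reasoning applies.

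**A repair that fails.** Cutting exposure at AE onset and putting the result through the median split shortens cases but not non-cases. With no stopping and no true effect, this gives AE rates of 15.6% (≤ median) vs 2.2% (> median) and 100% rejection under onset within the course, and 12.3% vs 6.9% and 59% under 30-day onset.

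**The case against.** The strongest reply is that these are exploratory tables in a surveillance study. The case number is set by regulation, the section headings speak only of possible influence, and no alpha or decision hangs on the rows. That stands, and it keeps the point below the most serious level. It does not dispose of it, because Section 1 names influencing factors as an aim and the plan gives no caution on reading these rows.

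Second, recording the action taken shows that an AE may stop treatment, not that it often does. This also stands. At 5–10% stopping the test is close to nominal, and a reader who took 75% as the expected error rate would go beyond the document.

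Third, a reader might infer that the efficacy table must be wrong, with longer treatment appearing less effective. The SAP does not support that. It states no rule linking course length to follicular response and no maximum course; the protocol, not shown, may do so. Even granting a link, the sign can go either way.

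Fourth, daily dose at start answers a different question from total exposure. True, but it is fixed before the outcome. It is still not randomised, so any association remains observational.

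**Conclusion.** The point holds as a design weakness of moderate weight. Sections 5.7 and 5.8 treat whole-course duration and total dose as antecedents of outcomes that can shape them. For AEs the SAP's own data items show the route. For follicular growth the point is conditional on course length depending on response.

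The size cannot be derived from the SAP. Under the stated assumptions (600 women, 10% AE risk independent of duration, two-sided 0.05), the false-positive rate is near 5% when few AEs stop treatment. It is about 8–25% when a quarter do and 17–75% when half do; the lower ends belong to onset spread over 30 days, the upper to onset wholly within the course. If AE risk instead accrues per day on treatment, even the direction for AEs is not fixed.

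One might infer that the study's main results are compromised. They are not: the overall AE, ADR, SAE, effectiveness and pregnancy rates do not use the exposure factors.

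**What to change.** In sections 5.7 and 5.8:
- Remove total duration and total dose from the chi-square/Fisher tests and from the logistic regression.
- Show both by outcome descriptively, without a p-value, and note that the outcome may have determined them.
- Use daily dose at start as the tested exposure factor. It replaces average daily dose, which is computed from the two whole-course quantities.

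If a duration-related safety analysis is wanted, add to 5.7 either first-AE incidence per person-day at risk or a time-to-first-AE model. State a risk window that also covers AEs after the last dose, since 5.7 does not restrict AEs to treatment days. Write explicitly that exposure cut at AE onset serves only as time at risk, never as a covariate or in the median split.

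Cost: SAP wording and modest programming. Daily dose and administration dates (4.5) and AE onset dates (4.7) are already collected. Each model loses two tested factors, as one exposure factor takes the place of three.
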